Person-family dyads assigned to the control group will receive a protocol of minimally enhanced usual care, encompassing a print educational brochure and blank easy to complete advance directive. The educational materials include a 44-page brochure developed by the National Institute on Aging entitled “A Guide for Older People: Talking with your Doctor” and an easy-to-read advance directive. Control dyads will be told that they are participating in a study about communication in primary care. We chose an active control arm for several reasons: 1.) because providing an advance directive should be the standard of care even if it is often not ‘usual care’, 2.) to ensure that positive results can be attributed to the effectiveness of the intervention, and 3.) to mitigate perceptions among dyads randomized to the control group that they are not being offered anything beyond usual care.

Participants will be randomized to treatment group at the level of the person-family dyad, following block randomization within primary care clinician. Participants in both groups will be followed over a 24-month period. Outcomes will be assessed from remote or in-person patient and caregiver interviews at enrollment and follow-up telephone or web surveys at 6, 12, and 24 months; electronic health record portal activity; information about advance directive completion from electronic medical record; burdensome care at the end of life from family telephone or web survey and CRISP.

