5.5.3 ENROLLMENT, BASELINE, AND/OR RANDOMIZATION

Enrollment officially occurs at the time of providing informed oral consent. See section 5.5.2 for more information about remote processes including enrollment and baseline assessment via telemedicine. For patient and family participants, enrollment occurs prior to completing the baseline assessment and randomization. The date of study enrollment will be tracked and documented for each participant.

Most intervention research in primary care has relied on cluster-randomization at the level of the clinic, which leads to challenges in the interpretation of results due to practice-level imbalances and unmeasured contextual differences.⁶⁰ This study randomizes at the level of person-family dyad, which may lead to between-group spillover and attenuate observed intervention effects. However, as 31 (+/- 5) intervention dyads will be enrolled at each clinic (~4/month), we do not expect widespread changes to standard clinic workflows or practices. We believe the possibility of contamination is low as the intervention consists primarily of one-on-one contact between the interventionist and the person-family dyad, and there are no elements of the intervention that attempt to address clinicians' communication skill. Nevertheless, our analysis plan permits us to assess for the occurrence of contamination by evaluating whether there are changes over time in the control arm related to care processes, such as registration for shared access to the patient portal and advance directive completion. Dyad-level randomization will afford a more nuanced understanding of context and allow examination of group differences by primary care clinic.

Each person-family dyad will be randomized to treatment or control group in a 1:1 ratio using stratified, blocked randomization by doctor with alternating block sizes of 4 and 6 for each clinician.

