Randomization will utilize a statistical algorithm within REDCap developed by the project statistician that is unknown to study staff. The randomization module will generate random treatment group assignment of study participants for each participating clinician. Once patient and caregiver informed oral consent (**B4, C2**) have been received by study staff, research staff will initiate the randomization procedure within REDCap. Person-family dyads assigned to the treatment group will receive information about SHARE. Person-family dyads assigned to the control group will receive print materials about the control protocol (See 6.1.1).

Research staff responsible for the randomization protocol after the enrollment visit will be aware of participant assignment status after it occurs. Allocation concealment will be ensured by blinding the PI and research staff conducting follow-up assessments and those responsible for coding study outcomes throughout the study. Only the study statistician, selected unblinded staff (and REDCap administrator),

and members of the data and safety monitoring board (DSMB) will have access to unblinded data before study completion. As randomization occurs at the level of the person-family dyad, clinicians will care for patients in both groups. Clinicians will be blinded to group assignment.

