6.3 MEASURES TO MINIMIZE BIAS

Most intervention research in primary care has relied on cluster-randomization at the level of the clinic, which leads to challenges in the interpretation of results due to practice-level imbalances and unmeasured contextual differences.⁶⁰ This study randomizes at the level of person-family dyad, which may lead to between-group spillover and attenuate observed intervention effects. However, as as many as 31 intervention dyads (+/- 5) will be enrolled at each clinic (~4/month), we do not expect widespread changes to standard clinic workflows or practices. We believe the possibility of contamination is low as the intervention consists primarily of one-on-one contact between the advance care planning facilitator and the person-family dyad, and there are no elements of the intervention that attempt to address clinicians' communication skill. Nevertheless, our analysis plan permits us to assess for the occurrence of contamination by evaluating whether there are changes over time in the control arm related to care processes, such as registration for shared access to the patient portal and advance directive completion.

Dyad-level randomization will afford a more nuanced understanding of context and allow examination of group differences by primary care clinic.

Each person-family dyad will be randomized to treatment or control group in a 1:1 ratio using stratified, blocked randomization by doctor with alternating block sizes of 4 and 6 for each clinician. A statistical program developed by the project statistician and unknown to study staff will be used to prospectively generate random treatment group assignment of study participants for each participating clinician. A set of opaque envelopes will be prepared for each clinician following the results of the statistical program. Upon providing informed oral consent (**B4, C2, D4**) and after completing the baseline enrollment survey (**B6, C3**), research staff will open the next sequentially ordered envelope specifying treatment group by clinician. Person-family dyads assigned to the treatment group will receive information about SHARE. Person-family dyads assigned to the control group will receive print materials about communicating with their doctor.

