9.2 SAMPLE SIZE DETERMINATION

Sample size is based on our ability to detect a clinically meaningful effect for our primary outcome at 6 months, following intention to treat. Because we randomize at the individual level, clinic-level cluster effects are not included in power calculations. From prior trials we assume an unadjusted intervention effect of 0.30 standard deviation units (SDUs).^{51,84} Incorporating baseline QOC scores as a covariate and assuming correlation of 0.65 between baseline and 6-month QOC scores yields a covariate-adjusted effect size of 0.39 SDUs. Based on an enrolled sample of about 248 dyads and attrition of 10%, a retained sample of 222 will provide more than 80% power to detect a covariate-adjusted effect of 0.39 using a two-sided test and a type 1 error rate of 0.05. For secondary outcomes, studies in similar samples^{25,57-59} suggest 50% mortality by 24 months. With 124 observations, power exceeds 80% to detect decreases of 20% or more in burdensome care (e.g. 30% vs. 10%). Assuming 25% attrition, 92 surrogate responses will be sufficient to monitor the effects of SHARE on satisfaction with end-of-life care, surrogate decision-making, and bereaved family outcomes; measures that are essential to assessment of quality of end-of-life care, as well as provide effect sizes to guide future trials of advance care planning in primary care populations.

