9.4 STATISTICAL ANALYSES

9.4.1 GENERAL APPROACH

Quantitative Strand. The objective of this study is to test the efficacy of SHARE on quality of communication (QOC) at 6 months. Analyses will be performed using SAS statistical software, with each dyad as the unit of analysis. We will use intention-to-treat analyses as the primary method of analysis; data from all participants will be analyzed as members of their assigned study group. **Primary outcome:** We will test the effects of SHARE on improved QOC compared to usual care at 6 months. We will use hierarchical analyses of covariance on the 6-month (**B7, C4**) QOC score with treatment group as the primary independent variable and baseline QOC score as the primary covariate. Other baseline characteristics (individual- or practice-level variables) will be covariates if there is imbalance on these measures by treatment group or if they are significantly correlated with 6-month QOC after adjusting for baseline QOC score. A multilevel design will be implemented using SAS Proc MIXED with dyads (level 1) nested within clinics (level 2) that will allow us to enter and control for clinic-level covariates (size and characteristics of patient panel, staff, location). **Secondary outcomes and supplemental analyses:** In addition to the primary outcome, numerous comparisons will be conducted for secondary outcomes, measures of implementation, and supplemental analyses for clinically relevant subgroups and maintenance of effects at 12 and 24 months. We will examine the maintenance of intervention effects at 12 (**B8, C6**) and 24-months (**B9, C7**) by extending the multilevel model to include a longitudinal or within-person level, and trajectories of treatment impact over time will be estimated with linear longitudinal models.

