9.4.2 ANALYSIS OF THE PRIMARY ENDPOINT(S)

Our sample encompasses persons with cognitive impairment, some of whom may be unable to respond to study assessments. Therefore, primary outcomes at 6 months are assessed from the perspective of the family caregiver, although all measures are fielded in parallel to patient and analyses will be conducted in parallel to examine both perspectives. Baseline enrollment visits and assessments are conducted after obtaining informed oral consent. Follow-up assessments are conducted by telephone by study staff to afford greater flexibility and privacy. Caregivers are offered the opportunity to complete web-based follow-up assessments. Composite outcomes will be operationalized as previously described in source analyses of the psychometric properties of each battery. The outcomes that we assess have been identified as defining success in advance care planning and for which strong measures now exist.^{135,136} We examine two primary outcomes, as follows:

Quality of Communication. We assess family caregiver-reported quality of communication at 6 months, using the end-of-life subscale (n=7 items) of the validated instrument.^{137,138} The QOC has excellent internal consistency and strong evidence of reliability and validity: we focus on the end of life subscale which is most pertinent to advance care planning in the target population. We follow the question wording stipulated by Engelberg (2006), with two modifications. First, we have revised the question stem to reflect the perspective of the family. Second, we have revised the question stem to reflect our interest in communication with the primary care team as opposed to “their doctor”.

Satisfaction with Care at the End-of-Life in Dementia (SWC-EOLD) is a 10-item instrument measured on a 4-point Likert scale that ranges from 1 “strongly disagree” to 4 “strongly agree” with a summary score ranging from 10-40 in which higher values indicate higher satisfaction.^{90,139,140} We field this instruments as originally described by Volicer to bereaved family caregivers of patient participants who die by 24 months.

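### Minor: the primary 6-month QOC model has a clinic level but no term for clinician, the randomization stratum, so its reported SE may be slightly too large

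*Combined protocol and SAP*

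**What the plan says.** The clinician is the stratum throughout. Section 4.1 assigns dyads "following block randomization within primary care clinician". Section 5.5.3 specifies "stratified, blocked randomization by doctor with alternating block sizes of 4 and 6 for each clinician" and adds: "The randomization module will generate random treatment group assignment of study participants for each participating clinician". Section 6.3 describes the same stratum: "A set of opaque envelopes will be prepared for each clinician".

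The primary analysis in section 9.4.1 is a hierarchical analysis of covariance on 6-month QOC, with "treatment group as the primary independent variable and baseline QOC score as the primary covariate". Its levels are "dyads (level 1) nested within clinics (level 2) that will allow us to enter and control for clinic-level covariates". Further individual- or practice-level covariates enter only if they are imbalanced between arms or correlated with the outcome. No fixed or random effect for clinician appears in 9.2, 9.4.1 or 9.4.2.

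On clustering, section 9.2 says only this: "Because we randomize at the individual level, clinic-level cluster effects are not included in power calculations". It does not mention clinician effects.

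**The concern.** Blocking within clinician makes the arms nearly equal in size for each clinician, so differences between clinicians almost cancel in the treatment contrast. A model that omits the stratum does not know this. It counts clinician variance as residual noise and reports a standard error that is too large. The clinic level is no substitute, because it does not separate clinicians who work in the same clinic.

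At stake is a primary confidence interval slightly wider than the design warrants and a slightly conservative test. The point estimate and the protection against false positives are not in question.

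**Working it through.** **1. The plan's own power.** Inputs from section 9.2: unadjusted effect 0.30 SD, baseline to 6-month correlation 0.65, 248 dyads enrolled, 10% attrition, 222 retained, two-sided alpha 0.05.

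- Adjusted effect: 0.30/√(1 − 0.65²) = 0.30/0.760 = 0.395 (plan: 0.39).
- Retained: 248 × 0.90 = 223 (plan: 222, or 111 per arm).
- Power for 0.39: Φ(0.39 × √(111/2) − 1.96) = Φ(2.905 − 1.96) = 0.828. The noncentral t gives 0.825.

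The claim of more than 80% reproduces.

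**2. Upper bound on the effect.** Let ρ be the clinician share of the 6-month QOC variance left after baseline adjustment. With perfect balance and nothing absorbed by clinic, the true variance is (1 − ρ) times the one the model reports. The reported SE is then too large by 1/√(1 − ρ) − 1. At ρ = 0.10 this is 1/√0.90 − 1 = 5.4%. In practice it is less, because the clinic term absorbs some clinician variance, and incomplete blocks and attrition disturb the balance.

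**3. Assumptions the documents do not supply.** Clinician ICC 0-0.10 as defined above (0.10 is 0.10 × (1 − 0.65²) = 0.058 of total variance), clinic ICC 0.02, 20-45 clinicians, attrition at random. The documents differ on the number of clinics: up to 10 (section 1.1), up to 9 (section 4.1), and about 4 if 31 intervention dyads come from each clinic (section 5.5.3; 124/31 = 4). All three were used.

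**4. Simulation.** 248 dyads, alternating blocks of 4 and 6 within clinician, unequal panels, 222 retained, r = 0.65, effect 0.30 SD, REML, 6,008 runs per setting, with df equal to n minus the rank of the fixed and random design. The planned clinic-only model is compared with the same model plus clinician nested in clinic. Settings (clinics/clinicians) are 4/20, 9/20, 9/30 and 10/45.

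| Clinician ICC | SE ratio, planned/with clinician (four settings) | Power lower by (points) |
|---|---|---|
| 0 | 1.0037, 1.0031, 1.0040, 1.0051 | 0.1-0.2 |
| 0.02 | 1.0085, 1.0062, 1.0082, 1.0092 | 0.3-0.5 |
| 0.05 | 1.0183, 1.0128, 1.0158, 1.0165 | 0.5-0.9 |
| 0.10 | 1.0378, 1.0255, 1.0320, 1.0336 | 1.1-1.9 |

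The difference at ICC 0 is a boundary artefact of variance estimation and no real gain.

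At ICC 0.10, in the same order of settings:

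- Actual SD of the estimate, planned vs with clinician: 0.0960 vs 0.0957, 0.0982 vs 0.0980, 0.0987 vs 0.0986, 0.0979 vs 0.0979. The estimator is practically unchanged; only its reported SE differs.
- Power: 0.857 vs 0.875, 0.850 vs 0.862, 0.853 vs 0.864, 0.851 vs 0.862. Across all settings and ICCs the planned model has 82.5-85.7%.
- Type I error: 0.038 vs 0.044, 0.051 vs 0.053, 0.046 vs 0.053, 0.047 vs 0.054 (Monte Carlo SE 0.003; SE of the paired difference 0.0011-0.0013).

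**5. Second method.** The design-based variance was averaged over 400 randomizations per layout, for 4, 8 or 10 clinics with 3 to 10 clinicians each. Against the true SE, the clinic-only SE is too large by 0% at ICC 0, 0.4-0.7% at 0.02, 1.1-1.8% at 0.05 and 2.3-3.8% at 0.10. Against a clinician-intercept model the excess at 0.10 is 2.6-4.2%. Type I error at 0.10 is about 0.042-0.045.

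**6. Power cost of a 4% excess in the plan's own calculation.** Φ(2.905 − 1.96 × 1.04) = Φ(0.867) = 0.807, against 0.828: about 2 points.

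**7. Sensitivity to the ICC definition.** If 0.10 is read as a share of total variance, the baseline-adjusted value is 0.10/0.5775 = 0.173. The SE ratio is then 1.049-1.074 and the power difference 2.2-2.8 points. This lies outside the range used for the conclusion.

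**The case against.** The strongest reply is that both models are valid and the plan falls short of nothing it promises. The estimate is unbiased, and the planned model keeps more than 80% power in every setting examined. That stands, and it is why the point is minor.

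The documents also give reasons to expect a small ICC. Baseline QOC is the same scale, so it should absorb part of any stable clinician difference. Section 9.4.2 rewords the item stem to reflect "our interest in communication with the primary care team as opposed to" the individual doctor. Sections 5.5.3 and 6.3 say that nothing in the intervention targets clinicians' communication skill. Practice-level covariates may take up some of the same variance. These arguments favour the lower end of the range, but they do not show that the variance is zero.

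The largest simulated figures (3.8% and 1.9 points) come from the four-clinic setting, and section 6.3 treats 31 intervention dyads per clinic as a maximum, so four clinics is near a lower bound. With 9 or 10 clinics the simulation gives 2.6-3.4% and 1.1-1.2 points at ICC 0.10. The second method, however, reaches 3.8% against a clinician-intercept model with 8 clinics of 6 clinicians and even panels, so the upper end does not depend on four clinics alone.

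The conservatism of the test is also hard to see in three of the four simulated settings, where planned type I error at ICC 0.10 is 0.046-0.051. The direction rests on the paired differences and the design-based calculation. Its practical effect is very small.

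**Conclusion.** The omission is real: the trial randomizes within clinician, and the primary model has no clinician term. The consequence is a reported SE about 0-4% larger than with the term for a baseline-adjusted clinician ICC of 0-0.10. It stays under 1% at an ICC of 0.02, and the top of the range needs an ICC of 0.10. The cost in power is at most about 2 points. The size rests on assumed values for the clinician ICC, the number of clinicians and the clinic ICC, and on attrition at random. This is a minor, optional refinement that corrects no wrong conclusion.

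**What to change.** In section 9.4.1, before unblinding, add a random intercept for clinician nested in clinic to the primary Proc MIXED model for 6-month QOC and keep the clinic intercept, for example `RANDOM INTERCEPT / SUBJECT=clinic; RANDOM INTERCEPT / SUBJECT=clinician(clinic);`. State that if the clinician variance is estimated as zero, the fit reduces to the planned clinic-only model. In the simulation this happened in 58-61% of runs at ICC 0 and in 5-10% at ICC 0.10, so the sentence is needed. No change to other models is proposed.

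The cost is one RANDOM statement and one sentence. Assignment is generated by clinician (section 5.5.3), so the clinician is already recorded for every dyad. No new data and no change in sample size are needed.

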4 STUDY DESIGN

4.1 OVERALL DESIGN

This is a two-group single-blind randomized Phase 2 efficacy trial that will be conducted at up to 9 primary care practices in which 124 (+/- 10) dyads will receive a control protocol of minimally enhanced usual care and 124(+/- 10) dyads will receive usual care augmented with the SHARE protocol. We test the efficacy of multicomponent communication intervention, referred to as SHARE, on quality of communication (primary outcome) and advance care planning processes (secondary outcomes) at 6-, 12-, and 24-months

among primary care patients with cognitive impairment (mild-severe) and family caregiver dyads. For patients who die by 24 months, we examine the quality of end of life care (primary outcome) and bereaved family caregiver experiences with medical decision-making (secondary outcomes). Following enrollment and follow-up procedures, a small number of intervention group dyads will be selected to participate in a focus group interview to assess opinions and impressions of the SHARE experience. Primary care patients and family caregiver dyads will consent to being contacted for potential focus group participation.

SHARE encompasses usual care, supplemented with the following four therapeutic elements: 1) a letter from the practice introducing the initiative, 2) access to a designated staff member (e.g., medical assistant, social worker or nurse, community health worker, or lay facilitator) trained to lead advance care planning discussions, 3) person-family agenda-setting to align perspectives about the role of the caregiver and stimulate discussion about goals of care, and 4) education about communication and available resources, including a 44-page brochure developed by the National Institute on Aging entitled “A Guide for Older People: Talking with your Doctor”, a blank easy to complete advance directive, and facilitated registration to the patient portal (for patient and caregiver) to extend electronic interactions and information access to family. The control group will receive minimally enhanced usual care with print educational materials that include the 44-page brochure developed by the National Institute on Aging entitled “A Guide for Older People: Talking with your Doctor” and a blank easy to complete advance directive.

[figure not shown]

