4.3 END-OF-STUDY DEFINITION

A participant is considered to have completed the study if he or she has completed the baseline, 6-month, 12-month, and 24-month assessments – or the bereavement survey, for family to patient participants who die prior to 24 months and/or completed a qualitative interview for those in the intervention. The Schedule of Activities (SoA) are shown in **Section 1.3**. If a patient/family dyad is lost to follow-up, we will

use all available data that are observed on that dyad in analyses. For patients who are lost to death, we will attempt bereavement surveys with family caregivers two to three months after death, following best practices.

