Research staff responsible for the randomization protocol after enrollment will be aware of participant assignment status after it occurs. Allocation concealment will be ensured by blinding the PI and research staff conducting follow-up assessments and those responsible for coding study outcomes throughout the study. Only the study statistician, selected unblinded staff (and REDCap administrator), and members of the data and safety monitoring board (DSMB) will have access to unblinded data before study completion. As randomization occurs at the level of the person-family dyad, clinicians will care for patients in both groups. Clinicians will be blinded to group assignment. Patient-family dyads will have knowledge of group assignment, but no delineation will be made between group assignment indicating which is treatment or control. We will use group naming conventions of (Group A and Group B) to describe group assignment.

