If a clinician drops out before randomization occurs, he/she will be replaced. If a clinician drops out after randomization, but patient/family dyads are evaluable, we will perform an intent-to-treat analysis for that dyad. If a patient/family dyad are lost to follow-up, we will use all available data that are observed on that dyad in analyses. For patients who are lost to death, we will attempt bereavement surveys (**C7**) with family caregivers two to three months after death, following best practices. Patients and/ or caregivers that are assigned to the intervention who have completed the study, including those who are lost to death, will be invited to share their experience with the intervention through a final qualitative telephone/ video interview. The following information, further detailed in the Schedule of Evaluations (see 6.1) will be collected:

- Quality of end-of-life care, receipt of burdensome care at the end of life
- Surrogate decision-making experience (decisional conflict, decisional regret)
- Family caregiver symptoms of anxiety and depression
- Adverse events

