For dichotomous outcomes (e.g., newly documented advance directive; burdensome care) we will construct multilevel logistic regression models using SAS Proc GLIMMIX. We will compute the effect size of primary and secondary outcomes to assess SHARE effects relative to other treatment effect estimates for advance care planning interventions reported in the published literature. The multilevel model will also be used to examine potential intervention moderation effects by examining two-way interaction effects between intervention (SHARE vs. control) and either dyad (e.g., cognitive impairment, caregiving relationship) or clinic characteristics (e.g., size, urban vs. suburban/rural) in separate models. Given the relatively modest sample size available for some secondary analyses, careful attention must be given to potential problems such as over-parameterization; thus only a limited number of covariates will be included in these models and potential interactions will be examined in separate models. We will examine rates of recruitment and retention, the timeliness and completeness of collected data,¹³⁰ and relative attrition rates (SHARE versus control protocol).⁶⁰

Qualitative Strand. At the end of the study, we will assess the acceptability of SHARE and the mechanism of observed effects.^{131,132} From audio-recordings of advance care planning facilitation sessions we will examine the duration, content, and receptivity to components of SHARE. After the completion of 24-month interviews or at any point after enrollment, we will seek invite select group of 12-20 dyads, all ACP facilitators and ACP fidelity raters to complete post-intervention in-depth interviews. These interviews will be audio-recorded, transcribed verbatim, and entered into NVivo 9 textual data analysis software. Qualitative analyses will be conducted by the study team concurrent to data collection using a framework approach^{132,133} involving familiarization with content, identification of a thematic analytic framework, data indexing, charting to abstract and distill key themes, and the mapping of charts to interpret themes and context-specific meaning. We will ensure rigor and minimize bias by comprehensively documenting data collection, regular study team debriefs, triangulation of diverse stakeholder perspectives and data

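### Section 9.4.1 permits qualitative interviews, in effect SHARE-only, before the 6-month primary survey, contrary to sections 4.1 and 8.1; section 4.3 also counts an interview towards completion in one arm only

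*Combined protocol and SAP*

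**What the plan says.** Four places in the combined protocol and SAP bear on when the interviews happen and who has them.

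- **Section 9.4.1, Qualitative Strand:** "After the completion of 24-month interviews or at any point after enrollment, we will seek invite select group of 12-20 dyads". The same sentence goes on to "all ACP facilitators and ACP fidelity raters to complete post-intervention in-depth interviews". It does not name the arm of the dyads.
- **Section 8.1, Completion/Final Evaluation:** patients and caregivers "assigned to the intervention who have completed the study, including those who are lost to death, will be invited to share their experience" in a final telephone or video interview.
- **Section 4.1:** "Following enrollment and follow-up procedures, a small number of intervention group dyads will be selected to participate in a focus group interview".
- **Section 4.3:** completion is defined by the baseline, 6-, 12- and 24-month assessments, or by the bereavement survey, "and/or completed a qualitative interview for those in the intervention".

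The Schedule of Activities (section 1.3) has no row for the interview. The primary outcome (section 9.4.2) is the end-of-life subscale of the Quality of Communication (QOC) instrument, reported by the caregiver at 6 months.

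**The concern.** Sections 8.1 and 4.1 put the dyad contact after the study or after follow-up. Section 9.4.1 allows it at any time from enrollment. If 9.4.1 is followed as written, a SHARE caregiver can have an in-depth research conversation about the programme in the first months and then rate communication with the primary care team at month 6. That conversation is not one of the four SHARE components in section 6.1.1, and controls have no counterpart. Any shift it caused in a subjective rating would be counted as an effect of SHARE.

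The completion definition is a second and smaller matter. Through its and/or wording, section 4.3 gives intervention participants a route to completer status that controls do not have. Section 9.4.1 plans to compare retention and relative attrition between the arms, so completion should mean the same thing in both.

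**Working it through.** **Is the early contact permitted, and is it SHARE-only?**

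1. The open timing in 9.4.1 governs the whole list: dyads, facilitators and raters. Nothing in the sentence exempts dyads or bars a date before the 6-month survey.
2. The label post-intervention in that sentence does not supply a bar. Section 6.1.2 tailors follow-up contacts to the dyad and gives no end date for SHARE.
3. Section 8.1 is not a firm bar either. It relies on having completed the study, and 4.3 can be read to let the interview itself contribute to completion.
4. That the dyads are SHARE dyads is an inference for the 9.4.1 sentence. It is well supported: 4.1, 4.3 and 8.1 all name the intervention group, and the strand's stated aim is the acceptability of SHARE. Section 4.1 speaks of a focus group, which may be a separate activity, so 8.1 is the closer match.

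**The plan's own figure**

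Inputs from section 9.2: 248 dyads enrolled, 10% attrition, 222 retained (222/2 = 111 per arm), unadjusted effect 0.30 SD, baseline to 6-month correlation 0.65, two-sided alpha 0.05.

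- Adjusted effect = 0.30/√(1 − 0.65²) = 0.395 (plan: 0.39).
- Retained = 248 × 0.90 = 223.2 (plan: 222).
- Power = Φ(0.39/√(2/111) − 1.96) = Φ(2.905 − 1.96) = 82.8%. The plan's claim of more than 80% is reproduced and is not in dispute.

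**How large could the effect be?**

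Share of the arm: 12/124 = 9.7% and 20/124 = 16.1% of those enrolled; 12/111 = 10.8% and 20/111 = 18.0% of those retained.

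The documents give no effect of an interview on QOC. I assume a shift of 0.1–0.5 SD in interviewed dyads, always in favour of SHARE, and that every interview precedes the 6-month survey.

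- Movement of the SHARE mean, m = (k/111) × shift, where k is the number of interviewed dyads.
- With no true effect, let b = m/√(1 − 0.65²) and se = √(2/111) = 0.134. The two-sided rejection rate is 1 − Φ(1.96 − b/se) + Φ(−1.96 − b/se).

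| Assumed shift | m, 12 dyads (share of 0.30 SD) | Rejection rate | m, 20 dyads (share of 0.30 SD) | Rejection rate |
|---|---|---|---|---|
| 0.1 SD | 0.011 SD (4%) | 5.1% | 0.018 SD (6%) | 5.4% |
| 0.2 SD | 0.022 SD (7%) | 5.5% | 0.036 SD (12%) | 6.4% |
| 0.3 SD | 0.032 SD (11%) | 6.2% | 0.054 SD (18%) | 8.3% |
| 0.5 SD | 0.054 SD (18%) | 8.3% | 0.090 SD (30%) | 14.3% |

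The range is therefore about 0.01–0.09 SD. At a shift of 0.2 SD or less the rejection rate stays at or below 6.4%.

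**The case against.** The best reply is that most of the text points to late interviews. Section 8.1 calls the interview final, 9.4.1 opens the strand at the end of the study, and open timing is natural for facilitators and raters. No passage schedules a dyad interview in the first six months. The size calculation rests on an assumed shift, and its top value exceeds the 0.30 SD assumed for the whole programme. The outcome rates communication with the primary care team, which a research interview is not. SHARE dyads may already have other arm-specific research contact, such as the brief questionnaires after facilitator meetings (section 6.1.2). All of this stands. It limits the likely size but does not remove the contradiction.

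Two stronger readings are tempting, and the documents support neither.

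- **Inflated retention.** A reader might infer from 4.3 that SHARE retention would be overstated by 9.7–16.1 percentage points. That needs every interviewed dyad to give an interview yet lack its final survey, and needs the attrition comparison to use the 4.3 definition. Section 9.4.1 does not say that it does. Section 7.3 defines loss to follow-up by failed attempts to contact a participant for the surveys, identically in both arms.
- **Unblinding.** A reader might set "Qualitative analyses will be conducted by the study team concurrent to data collection" against "Allocation concealment will be ensured by blinding the PI and research staff conducting follow-up assessments" and infer that transcripts would unblind those staff. Section 10.1.3 keeps identifying information off interview recordings and transcripts. Section 10.1.9.1 has masked staff carry out follow-up and record extraction, and 10.1.8 has a blinded team member adjudicate survey responses. Nothing says that the PI or the outcome assessors do the coding.

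**Conclusion.** The point holds as an unreconciled contradiction on timing with a modest risk to the primary comparison. Read literally, 9.4.1 lets a SHARE-only research contact precede a subjective primary outcome. Whether that would happen is unknown. The upper end of the calculated range requires 20 interviews, all before month 6, each moving the caregiver's rating by 0.5 SD in favour of SHARE; a realistic effect is probably near the lower end.

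The 4.3 wording is a separate defect of definition. The primary analysis is by intention to treat (9.4.1) and dyads lost to follow-up contribute all their observed data (4.3), so that analysis does not depend on completer status. Reported completion counts could nevertheless mean different things in the two arms.

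**What to change.** 1. **Section 9.4.1:** state that no dyad is interviewed before its own 6-month survey is done or, if that survey is missed, before its window has closed. Tie the rule to the dyad's survey rather than to a calendar date, because the follow-up window is ±30 days in section 1.3 but appears as both ±30 and ±90 days in section 8.1. Facilitator and fidelity-rater interviews can keep flexible timing.
2. **Sections 4.1 and 8.1:** align them with the rule chosen, and say whether the focus group and the individual interview are one activity or two.
3. **Section 4.3:** delete the clause on the qualitative interview, so that completion is defined identically in both arms.

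The cost is wording only. Sample size and power (82.8%) do not change. A stricter alternative is to interview dyads only after study completion, as 8.1 already says. That would also protect the 12- and 24-month and bereavement outcomes. Its price is the loss of some accounts to death, decline or poorer recall, in patients aged 80 or older with cognitive impairment and an assumed 50% mortality by 24 months (section 9.2). Either choice is defensible; leaving the sections in conflict is not.
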